4.3. PD-1 (Programmed Cell Death 1) receptor and its inhibition

PD-1 is a key immune inhibitory receptor present on the surface of T lymphocytes that on binding to programmed cell death ligands (PD-L1 or PD-L2) on tumour cells or antigen presenting cells, results in a negative T cell effector immune response. Phase I studies assessing efficacy of anti-PD-1 antibodies, including nivolumab, have shown anti-tumour efficacy in melanoma, renal cell carcinoma, and lung carcinoma; these tumours were found to have upregulation of PD-L1 on cell surfaces. This suggested that disruption of the PD-1/PD-L1 signalling pathway mediated the objective response of the anti-PD-1 antibody. Several recent clinical studies of nivolumab and pembrolizumab showed impressive response rates and significantly increased overall survival in melanoma and non-small cell lung cancer patients, leading to FDA and TGA approval for these agents.

4.4. Pembrolizumab

Pembrolizumab (MK3475, formerly known as lambrolizumab), is a fully humanized humanised monoclonal IgG4-kappa isotype antibody against PD-1. A Phase I study of pembrolizumab confirmed safety and tolerability at doses of 1 mg/kg, 3 mg/kg and 10 mg/kg administered intravenously every two weeks, with maximal tolerated dosing not reached, and efficacy demonstrated in all dose levels. Subsequently, data from a Phase I study expansion cohort of melanoma patients receiving 10 mg/kg every 2 weeks, 10 mg/kg every 3 weeks or 2 mg/kg every 3 weeks showed equivalent response rates across all three cohorts, with significantly reduced toxicities in the latter two groups of 4% and 9% respectively. More recently, a Phase I study of pembrolizumab in non-small cell lung cancer patients, previously treated or untreated, revealed objective response rates of 19.4% in unselected patients, versus 45% in those with greater than 50% of PD-L1 expression; in this enriched population, the median progression free survival was 6.3 months, with overall survival not reached (Garon 2015).

In a long term follow up study of patients who had received the anti-PD1 antibody BMS-936558, one patient with metastatic colorectal cancer patient, of MSI high subtype, undergoing intermittent dosing of BMS-936558 achieved a complete and prolonged response, remaining disease free at 3 years (Lipson 2013). Subsequently, a Phase II study showed that pembrolizumab (at 10 mg/kg administered intravenously 2 weekly) increased progression free survival in microsatellite unstable metastatic colorectal cancer patients with a disease control rate of 90% and overall response rate of 40%. Unfortunately, results from this study, in addition to previous first in human Phase I anti-PD-1 antibody trials revealed minimal response rates in patients with microsatellite stable disease, which comprises the majority of colorectal cancers (Le 2015).

Data from preclinical models suggest that colorectal cancers could potentially be converted to a more “immunogenic” cancer type through priming of the immune system e.g. following radiation or vaccine therapy, leading to increased responses to check point inhibitors and immunomodulation (Dovedi 2014; Cross 2015; Gerber 2014). Thus, the

combination of anti-PD1 therapy and mutant RAS peptide vaccine therapy may be a promising strategy.

4.5. Locally Advanced Primary and Recurrent Colorectal Cancer

Neo-adjuvant chemoradiation prior to total mesorectal excision is considered the standard of care in patients with locally advanced rectal cancer where R0 resection can be expected, with significant improvements in long term overall survival rates over the past two decades. Chemoradiotherapy, either conventional or short course (CRT or SCCRT), is usually given as neoadjuvant treatment. Standard total mesorectal excision should achieve a curative resection. The use of CRT or SCCRT aims to reduce local recurrence (Glynne-Jones 2017). Despite this, 5-20% of these patients will experience local recurrence, at which time, their disease is more often than not incurable, with five year survival rates reported between 13% and 47% (Rahbari 2011).

Patients presenting with pelvic disease recurrence are often considered for resection, including aggressive radical debulking surgery or pelvic exenteration, which is associated with significant operative risks. Pre-operative re-irradiation may be offered prior to resection in selected patients, however, late toxicities are of concern with some patients not being suitable candidates. A recent publication evaluating five year survival rates of patients who achieved an R0 resection was 39% compared to only 22% in patients who were treated without surgery or underwent subtotal tumour removal.

Routinely there is a period of more than 8 to 12 weeks between diagnosis and resection and treatment of locally advanced disease or recurrence to resection according to the usual practise of the hospital, which allows a window of opportunity for patients to undergo systemic therapy (e.g. with vaccination and/or check point inhibition) whilst awaiting surgery. As per [Figure 1](#), patients will be consented for the trial at the time of the diagnosis of the disease recurrence, once they have completed other anti-cancer therapy as applicable (such as radiotherapy/chemoradiotherapy).

The presence of locally advanced disease or recurrence will be confirmed by appropriate diagnostic imaging (the actual types of scans and other tests can vary in different institutions and this protocol does not define the nature of these tests) as per standard clinical practice at each hospital.

This provides justification for evaluation of TG02, with or without PD-1 inhibition, in patients with newly diagnosed locally advanced primary and recurrent colorectal cancer prior to radical surgery.

This is a window of opportunity study and, because surgery will not be delayed as a result of the TG02-treatment, it is not expected that the immunotherapy will have any direct benefits on the outcomes of surgery or the rate of cure. In the time that the patient is normally expected to wait from the time of the diagnosis and treatment of their disease and the time of surgery there is an opportunity to see what effect immunotherapy with this specific RAS vaccine has in eliciting a specific intra-tumoural T cell response.

While it would not be anticipated that any clinically relevant changes to tumour size would occur as a result of vaccination alone the ability to generate RAS specific T cells is important for two principal reasons: 1. The finding of cytotoxic T cells in the tumour will provide a rationale for vaccination overall and 2. It would add weight to the argument that

even if R0 resection is possible, adjuvant immunotherapy might be an important addition to other therapy post-surgery, which may enhance disease-free and overall survival.

4.6. Rationale for the study

Patients with locally advanced primary and recurrent colorectal cancer are often considered for radical pelvic surgery. This “window” allows an opportunity to use RAS peptides to induce an immune response and study whether this promotes a cytotoxic T-cell infiltration into the tumour and induce histologically at least tumour cell death. TG02-treatment alone or in combination with a PD-1 inhibitor, given prior to resection in patients with locally advanced primary and recurrent colorectal cancer may stimulate this immune response and provide evidence that vaccination with TG02 peptides induces enhanced specific T-cell tumour killing and this provides an important therapeutic intervention in the treatment of colorectal cancer. The hypothesis that there may be a requirement for a PD-1 inhibitor to facilitate the immune response induced by the TG02 vaccination is supported by the preliminary data from Part 1 of the study. The data suggest that PD-1 expression is seen on the cytotoxic T-cells as well as the T-helper cells in the peripheral blood as well as PDL-1 and PD-1 expression is seen on T cells in the surgical specimens. These results may indicate that the tumours would possibly respond to the addition of a PD-1 inhibitor.

4.7. Rationale for dose

The traditional approach to dose selection for cytotoxic anticancer agents is to escalate the dose until dose limiting toxicity. This concept of maximum tolerated dose is not applicable for peptides that generally lack any inherent toxicity and that are for local administration in the skin. TG02 is for induction of cellular immune responses, and consequently the immune response rate is the most important parameter to consider for determining an appropriate dose.

The rationale for the dose is based on studies performed with its precursor vaccine, TG01, which contains 7 of the 8 mutant RAS peptides present in TG02. The rationale for selecting the dose of 0.1 mg of each peptide per administration stems from the observations from a dose exploring study in colorectal cancer patients (CTN RAS 97005). In this trial the patients were first given four weekly administrations of a single RAS peptide at the dose of 0.1 mg per administration and subsequently, after three weeks rest, four weekly administrations of 0.3 mg peptide. An additional dose of 0.1 mg peptide was administered without GM-CSF at a separate site to elicit DTH. Indeed, more immune responders were seen after the second cycle, 13 versus 7 after the first cycle. Other studies with constant dose (0.1 mg per peptide) have demonstrated a similar increase in number of recorded immune responders after administration of boosters after the initial 4 week cycle. In a study with a cocktail containing four RAS peptides (dose 0.10 mg per peptide) in patients with advanced pancreatic cancer (CTN RAS 97004) the number of DTH responders was increased from 11 after the initial 4 week cycle, to 16 responders after only two additional administrations (week 6 and 10). This suggested that the 0.10 mg and 0.30 mg per peptide were immunologically equivalent in the CTN RAS 98005 study and that increasing the TG01 dose beyond the current 0.7 mg dose (0.1 mg per peptide) is unlikely to heighten further the levels of specific immune responses. Alternatively, reducing the TG01 dose to levels lower than 0.1 mg per peptide may result in sub-optimal T cell responses.

Given the acceptable safety profile and levels of T cell responses observed to date with the current dose of 0.7 mg (0.1mg each peptide) of TG01 , the clinical development of TG02 will commence using the same dose for each peptides (0.1 mg) with a total TG02 dose of 0.8 mg. TG02 will be given together with GM-CSF as immunomodulator. Please see the TG02 Investigators Brochure (IB) for more information.

4.8. Rationale for dose regimen

TG02

TG02 given in the TG02-treatment will be administered to the patient at week 1, 2, 3, 4, and 6. If surgery is scheduled after week 10 one more TG02-treatment will be given in week 10. In addition to this TG02 will at certain time points (week 1, week 4, week 6, week 8 and possible week 10), be administered intradermally (without prior administration of GM-CSF) as a DTH test to evaluate the immunological response. The rationale for this regimen is based on the results from the previous and ongoing studies with TG01/GM-CSF that demonstrate that prevailing RAS mutation specific T cells responses are induced in cancer patients after 4-6 weeks of vaccination.

Pembrolizumab

Although the licensed dosing regimen for pembrolizumab is 3-weekly, in this window of opportunity study there is limited time between the start of TG02 vaccinations and surgery. Also, in order that the scheduling of study visits can be minimised to avoid extra patient visits, it is proposed to administer the pembrolizumab 2-weekly. Based on the data reported from the KEYNOTE 006 study for melanoma (Schachter 2017), the efficacy was similar between the 2-weekly and 3-weekly schedule with very similar safety profiles. Additionally, time needs to be allowed for a TG02 specific immune response to be induced; therefore, pembrolizumab will be started at week 4 and continued two-weekly until surgery

5. STUDY OBJECTIVES

Primary Objectives:

- To determine the safety of TG02-treatment
- To evaluate the systemic TG02 specific immune responses and to investigate tumour T cell infiltration in tumour specimens

Secondary Objectives:

- To investigate changes in immunological and pathological markers in tumour tissue
- To investigate changes in FDG PET-CT images
- To investigate changes in CEA

Exploratory Objectives:

- To investigate changes in circulating tumour cells and/or circulating tumour DNA
- To investigate the functionality of RAS mutation specific T cells in tumour tissue and peripheral blood

6. STUDY DESIGN AND DESCRIPTION OF THE STUDY

This is a non-randomised open labelled Phase Ib exploratory study to investigate the safety and immune responses of TG02-treatment.

The study is divided into two parts, where after Part I the sponsor will make a decision as to the initiation of Part II. Part II will start after Part I has been completed. Patients will only be allowed to participate in either Part I or Part II of the study.

Part I is designed to investigate the objectives of the study with TG02-treatment as monotherapy, and the Part II is to investigate TG02-treatment in combination with pembrolizumab. Part I and Part II will enrol approximately 4-6 and up to 10 patients respectively.

6.1. Endpoints

Primary endpoints:

- Safety:
 - Adverse events
 - Laboratory assessments
 - Vital signs
- Systemic immune responses assessed by:
 - TG02-specific DTH response
 - Presence of TG02 specific T-cells in peripheral blood
 - Change in intra-tumoural lymphocytes

Secondary endpoints:

- Immune suppression factors in tumour specimens
- Pathological responses and markers of apoptosis in tumour specimens
- Change in standard uptake values (SUV) assessed by FDG PET-CT
- Change in CEA

Exploratory Endpoints:

[figure not shown]
- Change in circulating tumour cells and/or circulating tumour DNA
- Functionality of RAS mutation specific T cells in tumour tissue and peripheral blood

6.2. Study Design

[figure not shown]
The patients with locally advanced primary and recurrent colorectal cancer will be considered for the study. A multi-disciplinary team (MDT) at the sites will coordinate the staging and work up of the patients and select appropriate patients for curative surgery. Selected patients for surgery will either receive chemo-radiation treatment (3-5 weeks) or have no further treatment before they are being consented for the study, see patient flow and timelines in [Figure 1](#).

Figure 1: Patient flow and timelines

Patient flowchart with pre-surgery chemo/radiation

Patient flowchart without pre-surgery chemo/radiation

[figure not shown]
The patient will be defined as on study from the date of signed informed consent until the end of study (EOS) visit which should be scheduled after surgery.

The study is divided into two parts, Part I followed by Part II if decision of such will be made by the sponsor. Part II may start when all safety data, systemic immune responses (Delayed-Type Hypersensitivity (DTHs)) and tumour material (analysed for intra-tumoural T cell infiltration) are available for 4-6 patients in Part I of the study. The sponsor, after input from the Steering Committee, will evaluate the data to assess safety and preliminary immune activity and efficacy of TG02-treatment, and make a recommendation to proceed or not to Part II of this protocol.

Patients from Part I will not participate in Part II.

[figure not shown]
The study design for Part I is shown in [Figure 2](#) and the study design for Part II in [Figure 3](#).

Figure 2: Study design graphics Part I

- 1: Core needle biopsy pre TG02-treatment.
- 2: Tumour tissue at resection, at time of surgery.
- 3: If no surgery before week 10, a TG02-treatment will be given.
- 4: Only to be taken for patients who have surgery at week 10 or later and had a negative DTH outcome at week 8.
- 5: If surgery is after week 10, a sample will be taken as close as possible to surgery.

Figure 3: Study design graphics Part II

- 1: Core needle biopsy pre TG02-treatment.
- 2: Tumour tissue at resection, at time of surgery.
- 3: If no surgery before week 10, a TG02-treatment will be given.
- 4: Only to be taken for patients who have surgery at week 10 or later and had a negative DTH outcome at week 8.
- 5: If surgery is after week 10, a sample will be taken as close as possible to surgery.
- 6: If surgery is scheduled after Day50/Week 8, pembrolizumab will be given at Day 50/Week 8. If surgery scheduled after Day 64/Week 10, a further pembrolizumab infusion will be given at Day 64/Week 10.

Part I

Approximately 4-6 patients diagnosed with locally advanced primary and recurrent colorectal cancer will be given TG02-treatment for up to 10 weeks (up to 6 TG02-treatments) prior to surgery.

TG02 is an eight peptide vaccine. Significant clinical data exists for its precursor vaccine, TG01, which contains 7 of the 8 mutant RAS peptides present in TG02. TG01 in combination with GM-CSF has been shown to be immunogenic and well tolerated up to 11 weeks of treatment.

Since one of the eight peptides in TG02 has not previously been administered to humans, the first 3 patients will be enrolled in a sequential manner with a minimum lag time of 4 weeks between dosing of the first 3 subjects to ensure an acceptable safety profile.

The safety data collected during the first 4 weeks for the three first patients will be reviewed by a SSC consisting of Sponsor representatives, the Principal Investigator, relevant Sub-Investigators and one Independent Physician.

As a general rule the following will be reviewed to provide a guide to safety decisions:

Unacceptable toxicities will be defined as follows (based on NCI Criteria for Adverse Events (CTCAE) (v4.03: June 14, 2010) for reactions considered related to TG02 and/or GM-CSF:

- Injection site reaction of \geq grade 3 (grade 3: Ulceration or necrosis; severe tissue damage; operative intervention indicated, grade 4: Life-threatening consequences; urgent intervention indicated, grade 5: death).
- Other relevant clinically significant toxicity \geq grade 3 (excluding treatable nausea and vomiting). However, for certain toxicities such as laboratory assessments without a clear clinical correlate, a discussion in the SSC may take place to evaluate if this AE should be assessed as DLT.
- \geq Grade 3 'allergic reaction/anaphylactic reaction' in spite of prophylaxis with antihistamine and steroids.

All AEs and SAEs will be reviewed and will also be compared to those of the precursor vaccine TG01 (see Investigator's Brochure).

If more than 1 out of the 3 patients has DLT the SSC will review the nature of the events and make a final decision if the rest of the patients may be enrolled.

When all safety data, systemic immune responses (DTHs) and tumour material (analysed for intra-tumoural T cells infiltration) are available for all patients in Part I of the study, the sponsor, with input from the Steering Committee, will evaluate the data to assess safety and preliminary immune activity and efficacy to make the decision to proceed or not to Part II of this protocol. In Part II up to 10 new patients, not previously treated with TG02, will be recruited. No patients treated in Part I will be treated in Part II.

The SSC will review the tolerability of TG02-treatment in accordance with the SSC charter and this review will be based on an assessment of adverse events, laboratory

findings and, in particular the occurrence of hypersensitivity reactions. Toxicity grading will use NCI CTCAE version 4.03.

Part II

Up to 10 patients will be treated with TG02-treatment plus pembrolizumab for up to 10 weeks (up to six TG02-treatments and up to 4 pembrolizumab infusions) prior to surgery.

Again, since one of the eight peptides in TG02 is first in human, and that the use of pembrolizumab will be in a novel setting, as a precaution, the combination of TG02-treatment and pembrolizumab will be initiated first in 3 patients and evaluated for safety prior to subsequent recruitment of patients according to the same procedure as described above for Part I. The first 3 patients will be enrolled in a sequential manner with a minimum lag time of 6 weeks between dosing of the first 3 subjects to ensure an acceptable safety profile. The safety data collected during the first 6 weeks for the 3 first patients will be reviewed by the SSC.

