The treatment period will be from Day 1 (Week 1) and up to surgery, which is planned for week 8 but can occur in a window up to week 14. The following assessments will be performed on Day 1, Day 8, Day 15, Day 22, Day 36, Day 50 and if surgery is after week 10 (Day 64):

- Vital signs (heart rate, blood pressure and tympanic body temperature) and ECOG performance status
- Concomitant medications and adverse events will be monitored continuously
- Physical examination, haematology and serum biochemistry (Table 9-1) before treatment (Day 1) and during treatment on Day 15, Day 36, Day 50 and if surgery after week 10 (Day 64).
- TG02 treatment will be administered on Days 1, 8, 15, 22 and 36. If surgery after week 10 TG02 treatment will also be given at week 10 (Day 64).
- Pembrolizumab will be given on Days 22 and 36. If surgery is scheduled after Day 50/Week 8, pembrolizumab will be given at Day 50/Week 8. If surgery scheduled after Day 64/Week 10, a further pembrolizumab infusion will be given at Day 64/Week 10.
- DTH tests will be performed at baseline (Day 1), week 4 (Day 22), week 6 (Day 36) and week 8 (Day 50) (if surgery is scheduled for week 8 the DTH test should be performed two days before surgery). If surgery is after week 10, and the patient has had negative DTH tests up to and including week 8, an additional DTH test should be performed at week 10 (Day 64).

- Blood samples for in vitro assessment of TG02-specific immune responses (Immunology sample, PBMC) will be taken at baseline (Day 1) and Day 50. If surgery is after week 10, an additional sample should be taken as close as possible up to the date of surgery (see separate Immune monitoring plan).
- The CEA biomarker will be evaluated at Day 50. If surgery is after week 10 a third sample will be taken at Day 64 or just prior to surgery, whichever is the more appropriate.
- Tumour samples for assessment of immune response will be taken at time of surgery. If for any reason the patient will not have surgery a biopsy will be obtained if possible at the latest by week 14 (see separate Immune monitoring plan).
- FDG PET-CT scan for tumour assessment of standard uptake value (SUV-max) as close as possible up to date of surgery.
- Circulating Tumour Cells (CTC) will be evaluated at Day 1 and Day 50. If surgery is after week 10, an additional sample can be taken as close as possible up to the date of surgery.

Additional monitoring during the first 2 hours after any TG02-treatment:

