- d: Tumour tissue taken during resection. If for any reason, the patient will not have surgery a biopsy will be obtained if possible.
- e: To be done 2-0 days before surgery
- f: If surgery is scheduled for week 10, there will be no TG02-treatment given at week 10. If no surgery at week 10, the last TG02-treatment to be given at week 10.
- g: As close as possible up to the date of surgery.
- h: At the visits when TG02 and/or TG02-treatment (and pembrolizumab in Part II) is scheduled, the assessments should be performed prior to the treatments.
- i: Only to be taken for patients who have surgery after week 10 and had a negative DTH outcome at week 8. DTH (TG02) injection to be done 48 hours prior to surgery.
- j: Assessment of DTH (TG02) injection site to be done 48 hours (+/- 4 hours) after each DTH (TG02) injections by the patient in a study specific diary.
- k: Only applicable in Part II of the protocol
- l: To be done prior to surgery
- m: Allowed time for surgery (resection specimen) scheduled for week 8 is + 2 week and allowed time for surgery (resection specimen) scheduled for week 10 is + 4 week
- n: Blood samples for routine haematology and serum biochemistry to be recorded if already available in the patient medical record (standard of care)
- o: End of study visits to be scheduled during the hospitalized post-operative recovering period, up to 6 weeks after surgery.
- p: TG02-treatment is a combination of the two IMPs: GM-CSF and TG02. When TG02-treatment is administered, GM-CSF is to be given as an intradermal injection 15-30 minutes before the TG02 intradermal injection. GM-CSF and TG02 are administered as 2 separate intradermal injections, 15 to 30 minutes apart, at the same site in the upper arm. After any TG02-treatment the patients will be monitored for heart rate and blood pressure at 5, 10 and 30 minutes and then every 30 minutes thereafter for up to 2 hours post administration
- q: In addition, TG02 will, at certain time points, be administered intradermally (without prior administration of GM-CSF) in the lower area of the contra lateral arm as DTH test. The administration of GM-CSF (0.10 mL reconstituted GM-CSF) and TG02 (0.10 mL reconstituted TG02) has to be strictly intradermal.
- r: Should be within the last 4 weeks prior to first TG02-treatment.
- s: If surgery is scheduled after Day 50/Week 8, pembrolizumab will be given at Day 50/Week 8.

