- t: If surgery is scheduled after Day 64/Week 10, a further pembrolizumab infusion will be given at Day 64/Week 10.

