The drug handling of TG02-treatment will be described in a separate Study Drug Handling Plan.

Table 8-1: Treatment schedule

Time point	DTH test (TG02)	TG02-treatment (GM-CSF followed by TG02)	Pembrolizumab (Part II of the study)
Week 1	X	X	
Week 2		X	
Week 3		X	
Week 4	X	X	X
Week 6	X	X	X
Week 8	X*		X***
Week 10 (only if surgery is after week 10)	X**	X	X

*If surgery is scheduled to be done in week 8, DTH (TG02) injection to be done approximately 48 hours prior to surgery.

** Only to be taken for patients who have surgery at week 10 or later and had a negative outcome at week 8.

*** If surgery is taking place Day 51-63, pembrolizumab will be given at Day 50/Week 8.

Pembrolizumab: A fixed dose of 200 mg pembrolizumab will be administered as an intravenous infusion. Pembrolizumab should be administered according to the latest version of the Summary of Product Characteristics (SmPC), and dosed according to available guidelines for the use of this drug. Dependent on time of surgery, a patient will receive pembrolizumab 2 to 4 times throughout the treatment period.

All handling of the IMPs/drug products should be in compliance with normal handling of sterile products for injections.

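### For surgery in week 10, the design-figure notes give a sixth TG02-treatment that Table 6-1 footnote f and six other places do not

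*Protocol*

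**What the plan says.** Five TG02-treatments are common to all patients. Protocol 6.4.2 states: "TG02 treatment will be administered on Days 1, 8, 15, 22 and 36". A sixth, at week 10, depends on the timing of surgery, and the condition is worded differently in different places.

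- **Figures 2 and 3, note 3 (Protocol 6.2):** "If no surgery before week 10, a TG02-treatment will be given". The same note stands under both figures, so it covers Part I and Part II.
- **Table 6-1, footnote f (Protocol 6.4.4):** "If surgery is scheduled for week 10, there will be no TG02-treatment given at week 10", followed by "If no surgery at week 10, the last TG02-treatment to be given at week 10".
- **Protocol 4.8, repeated in 8.2:** "If surgery is scheduled after week 10 one more TG02-treatment will be given in week 10".
- **Protocol 6.4.2:** "If surgery after week 10 TG02 treatment will also be given at week 10 (Day 64").
- **Table 8-1 (Protocol 8.2), row label:** "Week 10 (only if surgery is after week 10").
- **Synopsis (study design, Part I) and SAP 3.2:** up to six treatments, the last one only where surgery takes place beyond week 10.

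Table 6-1 has a separate column for surgery in week 10, headed Day 64. Footnote m gives surgery scheduled for week 10 an allowance of a further 4 weeks.

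**The concern.** A patient whose operation falls in week 10 has not been operated on before week 10. Read as written, note 3 gives that patient a vaccination which footnote f withholds. Both are instructions to sites, and the schedule itself provides for this case.

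Two things are at stake. The first is exposure: whether a patient receives one more GM-CSF/TG02 administration around the time of resection would turn on which part of the protocol the site follows. The second is classification. SAP 5.1 summarises the number of injections and the total dose. SAP 4.4 has a treatment-deviation category, and SAP 4.2 removes patients with major deviations from the per protocol set. With two rules in force, giving or withholding the week 10 administration can be compliant under one and a deviation under the other.

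**Working it through.** **Inputs**

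- Fixed TG02-treatments: 5, on Days 1, 8, 15, 22 and 36 (Protocol 6.4.2).
- Possible further treatment: 1, at week 10, Day 64 (Protocol 6.4.2).
- Dose per injection: TG02 0.80 mg, GM-CSF 0.03 mg (synopsis).
- DTH injections are TG02 without GM-CSF and are not counted here.

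**The plan's own figure**

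Maximum number of treatments = 5 + 1 = 6. This agrees with the maximum of six in the synopsis and SAP 3.2.

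**Count by week of surgery**

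Treatments = 5, plus 1 if the week 10 condition is met. Note 3 is met when surgery is in week 10 or later. Footnote f and the other six places are met only when surgery is later than week 10. The scheduled and actual dates are taken to be the same.

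| Week of surgery | Note 3 | Footnote f | Synopsis, 4.8, 6.4.2, 8.2, Table 8-1, SAP 3.2 |
|---|---|---|---|
| 8 | 5 | 5 | 5 |
| 9 | 5 | 5 | 5 |
| 10 | **6** | **5** | **5** |
| 11 | 6 | 6 | 6 |
| 14 | 6 | 6 | 6 |

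**Cumulative vaccination dose for surgery in week 10**

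- TG02: 6 × 0.80 = 4.8 mg under note 3; 5 × 0.80 = 4.0 mg elsewhere.
- GM-CSF: 6 × 0.03 = 0.18 mg under note 3; 5 × 0.03 = 0.15 mg elsewhere.
- Ratio: 6/5 = 1.20, so 20% more of each under note 3.

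**Scheduled or actual date**

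The first sentence of footnote f, and the rule in 4.8 and 8.2, turn on when surgery is scheduled. Note 3 turns on whether surgery has taken place, and the synopsis and SAP 3.2 on when it occurs. Footnote m lets week 10 surgery move by up to 4 weeks. For a patient scheduled for week 10 and operated on later, the scheduled date points to five treatments and the actual date to six. No passage says which date governs.

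**The case against.** The strongest reply is that note 3 stands alone. Seven other places, including both schedule tables, agree with one another, and note 3 is a one-line annotation to figures that cannot be seen in the text available here. On the nominal calendar the extra administration would fall on the day of surgery itself, so the note may simply be loosely worded. A careful site might follow the majority. This bears on how often the discrepancy would be acted on and makes it easier to correct. It does not remove the instruction, which appears under both figures for a case with its own column in Table 6-1.

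A reader might also infer several larger faults. The documents do not support them.

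- **That week 10 means Days 64 to 70.** The synopsis, Figure 3 note 6, Protocol 6.4.2 and footnote t all equate week 10 with Day 64, and Table 6-1 puts Days 65 to 92 in the next column. The synopsis also pairs Days 51 to 63 with weeks 8 to 10, whereas a calendar-week count would end that span in week 9. The conflict therefore belongs to the Day 64 column, not to a whole week of surgery dates.
- **That footnotes f and t diverge, leaving a Part II patient with pembrolizumab alone.** Footnote t reads "If surgery is scheduled after Day 64/Week 10, a further pembrolizumab infusion will be given at Day 64/Week 10". On the protocol's own columns, surgery from Day 65 is after week 10 for both products. The divergence appears only if one meaning of week 10 is used for footnote f and another for footnote t.
- **That the pre-surgery PBMC sample is affected.** The third sample is taken only if surgery is after week 10. For Day 64 surgery the last planned sample is at Day 50, before any week 10 administration.
- **That the SAP needs a new exposure variable.** SAP 5.1 already summarises injections and total dose and lists all administrations, and SAP 4.7 lists all surgery data. With at most 16 patients, the count and the timing can be read from those listings.

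**Conclusion.** The inconsistency is real and narrow. For surgery in the Day 64 column, note 3 gives six TG02-treatments and seven other places give five, a difference of 0.8 mg TG02 and 0.03 mg GM-CSF. Before and after week 10 the rules agree.

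This rests on reading note 3 literally, on the protocol's equation of week 10 with Day 64, and on scheduled and actual surgery dates coinciding. Where they do not coincide, the unanswered question of which date governs adds a second ambiguity. The documents do not say how many patients will have surgery at week 10. Protocol 6.4.2 plans surgery for week 8, so the number may be small or zero. The point merits correction because it is an active dosing instruction, not because it threatens the study's descriptive conclusions.

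**What to change.** The sponsor should reconcile note 3 under Figures 2 and 3 with footnote f to Table 6-1, the synopsis, Protocol 4.8, 6.4.2 and 8.2, Table 8-1 and SAP 3.2, so that one condition for the week 10 TG02-treatment appears throughout. State that condition in study days. Say whether the scheduled or the actual surgery date governs, including for a patient whose week 10 surgery is moved within the allowance in footnote m. Which rule applies is a clinical decision for the sponsor, and this review takes no position on it.

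The cost is a wording amendment in a few places. It needs no extra visits, patients, samples or analyses.
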